9.6 Sample Size Calculation and Power Considerations

A total of 112 subjects (56 CINRYZE, 56 Placebo) will be randomized in a 1:1 ratio into 2 treatment groups: CINRYZE or placebo. Sample size was calculated for the primary endpoint and the key secondary endpoint using nQuery Advisor 7.0.

The primary endpoint in the study is the proportion of subjects with new or worsening TG at 6 months after treatment initiation. A 43% absolute difference in TG at 6 months between treatment groups (3/7 in placebo and 0/7 in CINRYZE) was observed in a subset of subjects (14/18) in the completed randomized Phase 2 pilot study (0624-201). For this study, the assumed proportion of subjects with new or worsening TG at 6 months will be 50% in the placebo group and 10% in the CINRYZE group. A sample size of 60 subjects (30 in placebo and 30 in CINRYZE) would be needed to obtain at least 90% power to detect a significant treatment difference at an alpha level of 0.025 (1-sided test).

The key secondary endpoint in the study is the proportion of subjects with all-cause graft failure. Assuming the proportions of subjects with graft failure due to AMR are 64% and 25% for placebo and CINRYZE, respectively, and all-other-cause graft failure rate is 12% for both placebo and CINRYZE, then the proportions of subjects with all-cause graft failure are 68% and 34% for placebo and CINRYZE, respectively. A total of 100 subjects will provide 90% power to detect an absolute treatment difference of 34% at an alpha level of 0.025 (1-sided test) for all-cause graft failure. These assumptions are based on literature ([Haririan et al. 2009](#); [Sharif et al. 2014](#); [OPTN/STRT Annual Data Report 2012](#)). Considering a 10% drop-out rate during the study, 112 subjects will be randomized to the study. Under these assumptions, the expectation is that there will be approximately 34 all-cause graft failures on placebo and approximately 17 all-cause graft failures on CINRYZE, giving 51 events total. The trial will continue until 51 such events are accrued and adjudicated by the nephrology EAC unless stopped prematurely based on findings at an interim analysis or until the final subject enrolled has been followed for 4 years post initial treatment with investigational product.

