## 2.5 Determination of Sample Size

A total of 112 subjects (56 CINRYZE, 56 Placebo) will be randomized in a 1:1 ratio into 2 treatment groups: CINRYZE or placebo. Sample size was calculated for the primary endpoint and the key secondary endpoint using nQuery Advisor 7.0.

The primary endpoint in the study is the proportion of subjects with new or worsening TG at 6 months after treatment initiation. A 43% absolute difference in TG at 6 months between treatment groups (3/7 in placebo and 0/7 in CINRYZE) was observed in a subset of subjects (14/18) in the completed randomized Phase 2 pilot study (0624-201). For this study, the assumed proportion of subjects with new or worsening TG at 6 months will be 50% in the placebo group and 10% in the CINRYZE group. A sample size of 60 subjects (30 in placebo and 30 in CINRYZE) would be needed to obtain at least 90% power to detect a significant treatment difference at an alpha level of 0.025 (1-sided test).

The key secondary endpoint in the study is the proportion of subjects with all-cause graft failure. Assuming the proportions of subjects with graft failure due to AMR are 64% and 25% for placebo and CINRYZE, respectively, and all-other-cause graft failure rate is 12% for both placebo and CINRYZE, then the proportions of subjects with all-cause graft failure are 68% and 34% for placebo and CINRYZE, respectively. A total of 100 subjects will provide 90% power to detect an absolute treatment difference of 34% at an alpha level of 0.025 (1-sided test) for all-cause graft failure. These assumptions are based on literature ([Haririan et al. 2009](#); [Sharif et al. 2014](#); [OPTN/STRT Annual Data Report 2012](#)). Considering a 10% drop-out rate during the study, 112 subjects will be randomized to the study. Under these assumptions, the expectation is that there will be approximately 34 all-cause graft failures on placebo and approximately 17 all-cause graft failures on CINRYZE, giving 51 events total. The trial will continue until 51 such events are accrued and adjudicated by the nephrology EAC unless stopped prematurely based on findings at an interim analysis or until the final subject enrolled has been followed for 4 years post initial treatment with investigational product.

Additional eligible subjects may be enrolled based on the interim data analysis of the first 30 subjects who complete the Month 6 TG assessment for the re-estimation of sample size.

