## 2.6 Multiplicity Adjustments for Type I Error Control

To control the overall Type I error, the primary and key secondary endpoint will be tested hierarchically with a fixed sequence approach. The study will continue to assess the key secondary endpoint only if the primary null hypothesis has been rejected. Thus, the significance of the key secondary endpoint is contingent, and no adjustment for multiple endpoints is needed.

The primary endpoint will have 2 analyses (1 interim and 1 final for the primary endpoint). The first interim analysis is for futility and sample size recalculation. The second interim analysis, which serves as the final analysis for the primary endpoint, is for the assessment of efficacy (new or worsening TG at 6 months). The alpha level of 0.0001 is to be spent at the first interim

analysis in developing the efficacy boundary of the second interim analysis of TG at 6 months. The overall significance level for the efficacy analysis of primary endpoint will be preserved at 0.025 (1-sided test) by using a significance level of 0.0249 for the second interim analyses. The difference between treatments will be evaluated by using the CHW weighted test statistic (Cui et al., 1999).

The key secondary endpoint will have 3 analyses (2 interim and 1 final), at approximately 50% (~26 events), 75% (~39 events) and 100% (~51 events) of the targeted all-cause graft failure. The Hwang-Shih-DeCani alpha spending function with phi = -4, which is similar to the boundaries from the O'Brien-Fleming method, will be used for the unequal spaced timing of analysis. Using this approach requires  $z \geq 2.75$  (or equivalently  $p \leq 0.0030$ ) to consider stopping the study for a positive treatment effect at the first interim analysis (~50% of events),  $z \geq 2.43$  (or equivalently  $p \leq 0.0075$ ) to consider stopping the study for a positive treatment effect at the second interim analysis (~75% of events), and  $z \geq 2.01$  (or equivalently  $p \leq 0.0221$ ) to claim efficacy at the final analysis (~100% of events), as shown in the table below. This approach maintains a fixed sample p-value close to 0.025 (1-sided test) at the final analysis and an overall significance level at 0.025.

Analysis	Proportion of Targeted Number of Events	Z Scale	p-value (1-sided)
Interim 3	50%	2.751	0.0030
Interim 4	75%	2.428	0.0075
Final	100%	2.012	0.0221

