### 10.1 Primary Efficacy Endpoint(s) and Analysis

The primary efficacy endpoint is defined as the proportion of subjects with new or worsening TG at 6 months post-treatment as adjudicated by the pathology EAC based on 2013 Banff criteria (standard score). New or worsening TG at 6 months by the standard score is defined as an increase of 1 or more between qualifying biopsy and 6-month biopsy. Subjects who do not have the TG assessment at 6 months post-dose will be assigned as failures, i.e. having ‘new or worsening TG’.

The primary analysis specified below will be performed based on the FAS for the first and second interim analysis of this study. As a sensitivity analysis, the primary analysis will be also performed based on Per-protocol Analysis Set-1 in the second interim analysis of the study.

The primary endpoint will be presented as the proportion of subjects with new or worsening TG determined at 6 months, and their difference between treatments (  $\Delta_{Cinryze-Placebo}$  ) is defined as follows:

$$\Delta_{Cinryze-Placebo} = \Pi_{Cinryze} - \Pi_{Placebo}$$

where  $\Pi_{Cinryze}$  is the proportion of new or worsening TG at 6 months post treatment in the CINRYZE group and  $\Pi_{Placebo}$  is the proportion of new or worsening TG at 6 months post treatment in the placebo group.

The analysis will employ a type I error rate of 0.025 to test null hypothesis:

$$H_0 : \Pi_{Cinryze} - \Pi_{Placebo} \geq 0$$

Against the 1-sided alternative:

$$H_a : \Pi_{Cinryze} - \Pi_{Placebo} < 0$$

There will be two interim analyses to assess the primary endpoint.

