## **APPENDIX 2 THE ALGORITHM OF DERIVING THE TG ASSESSMENT BY GRANULAR SCORE AND STANDARD SCORE**

### A. By Standard Score

Q6 on Final EAC Biopsy Assessment Form (New or worsening TG)		TG Assessment at Month 6 (Standard Score)
YES = Failure (Having new or worsening TG)		NO = No Failure
NO		NO
YES		YES
INSUFFICIENT DATA		YES

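### The stated 90% power for the primary endpoint makes no allowance for missing Month 6 TG readings, although the analysis counts each missing or insufficient reading as TG in both arms

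*SAP*

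**What the plan says.** SAP 2.5 and Protocol 9.6 size the primary endpoint in the same way. The assumed TG rates "will be 50% in the placebo group and 10% in the CINRYZE group". The conclusion drawn from these rates is that "A sample size of 60 subjects (30 in placebo and 30 in CINRYZE) would be needed to obtain at least 90% power". The level used is one-sided 0.025. The software is given as nQuery Advisor 7.0, but no test is named.

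The only attrition figure comes in the next paragraph, on all-cause graft failure: "Considering a 10% drop-out rate during the study, 112 subjects will be randomized to the study". It raises the key secondary number from 100 to 112. The primary paragraph has no counterpart.

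The missing-data rule is in SAP 10.1: "Subjects who do not have the TG assessment at 6 months post-dose will be assigned as failures", meaning they count as having new or worsening TG. Protocol 9.8.1 has the same rule. In SAP Appendix 2, part A, an adjudication of "INSUFFICIENT DATA" is also mapped to failure. Neither rule distinguishes between arms.

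The planned primary test in SAP 10.1 is Fisher's exact test within each stage, combined with CHW weights. A normal approximation replaces Fisher only when all four cells exceed 5. The type I error is kept "by using a significance level of 0.0249 for the second interim analyses". Protocol 9.8.1 triggers the analysis once 60 subjects complete the assessment; SAP 10.1 runs it on the FAS.

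**The concern.** A rule that counts missing readings as TG in both arms pulls the two rates together and raises the low CINRYZE rate most. Power worked out on 50% v 10% with every reading present therefore does not describe the analysis as written, unless those rates already contain the missing subjects. The plan allows for drop-out on the key secondary endpoint but states nothing for the primary endpoint.

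The primary test gates the trial. If it fails, SAP 10.1 claims futility, and under SAP 2.6 the key secondary hypothesis is not tested. A reader relying on at least 90% power at that gate needs to know which test and what level of missing readings the figure assumes.

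**Working it through.** **Inputs.** From SAP 2.5: 50% v 10%, 30 per arm, one-sided 0.025. From SAP 2.6: 0.0249 at the primary analysis. From SAP 10.1: missing equals failure, 15 per arm per stage, weights √(15/30). The missing fraction m is not in the documents, so a range is used. It is taken as equal in both arms and independent of TG.

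**Step 1: the plan's own figure, nothing missing.**
- Single one-sided Fisher test by exact enumeration: 29 per arm (58) reaches 90%, and 30 per arm gives 91.4%. The result is the same at 0.0249.
- Continuity-corrected formula: 31 per arm (62) needed; 89.7% at 30.
- Pooled Z formula: 26 per arm (52) needed. At 30 per arm the mean rate is 0.30, so the null standard error is √(2×0.30×0.70/30) = 0.1183 and the alternative standard error is √((0.25+0.09)/30) = 0.1065. Then (0.40 − 1.96×0.1183)/0.1065 = 1.58, or 94.3%. Exact enumeration gives 94.9%.

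Fisher and the continuity correction come within 2 subjects of 60, and pooled Z does not. Fisher is therefore a reasonable inference for the sizing test, but only an inference.

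**Step 2: apply the missing rule.** The analysed rate is p′ = m + (1 − m)p, so the difference becomes (1 − m)×40 points.
- m = 5%: 0.05 + 0.95×0.50 = 52.5% and 0.05 + 0.95×0.10 = 14.5%; difference 38 points.
- m = 10%: 55% and 19%; difference 36 points.
- The plan's 10% drop-out, spread evenly over 48 months, gives 10%×6/48 = 1.25% by Month 6 (1.3% in the table).

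**Step 3: power with the missing readings inside the 60** (exact enumeration; CHW with 15+15 per arm, 0.0249, no re-estimation and no futility stop).

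| Missing | Single Fisher, 30 v 30 | Pooled Z, 30 v 30 | Planned Fisher/CHW |
|---|---|---|---|
| 0 | 91.4% | 94.9% | 85.1% |
| 1.3% | 89.7% | 93.7% | 82.9% |
| 5% | 84.5% | 89.9% | 76.5% |
| 10% | 76.9% | 84.1% | 68.3% |

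Single Fisher drops below 90% at about 1.1% missing, and pooled Z (formula) at about 4.7%. Under the planned test, 15×0.10 = 1.5 CINRYZE events are expected per stage, so the condition that all cells exceed 5 is rarely met and Fisher governs in practice.

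**Step 4: power with the missing subjects added to 60 completers.** At 5%, 60/0.95 ≈ 63 subjects are analysed, or 31 to 32 per arm. Fisher gives 86.1% to 87.7% and pooled Z (formula) 90.7% to 91.6%. At 10%, 60/0.90 ≈ 67, or 33 to 34 per arm. Fisher gives 82.6% to 84.1% and pooled Z 87.5% to 88.5%.

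**Step 5: re-estimation.** SAP 10.1 raises the second stage when conditional power lies between a lower limit and 60%. The SAP leaves that limit to the DMC SAP. Assuming limits from 0 to 30% and at most 41 per arm in stage 2 (15 + 41 = 56, the planned arm size), enumeration at 5% missing gives about 73% to 89%, and 81% to 85% for limits of 10% to 5%.

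**The case against.** The strongest reply is that the drop to 84.5% rests on choices the documents do not make.

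- **Test.** A reader might infer that power falls to 84% for the very test used in sizing. No sizing test is named. With pooled Z, power at 5% missing is still about 90%.
- **Missing fraction.** A reader might take 5% as the plan's own expectation. It is not. The plan's only attrition figure, spread evenly, gives about 1.3% by Month 6 and costs single Fisher under 2 points.
- **Trigger.** The analysis is triggered by 60 completed assessments, so subjects without a biopsy may be additional to the 60, which gives 86% to 88% for Fisher at 5%. The lower figure needs the missing readings to lie within the 60, for example as insufficient biopsies.
- **Assumed rates.** A reader might conclude that the sizing takes every reading to be present. The rates are given for the endpoint as defined, which may already include missing-as-failure. The pilot's 3/7 and 0/7 with 10% missing would become 0.10 + 0.90×3/7 = 48.6% and 10%, close to 50% and 10%.
- **Re-estimation.** It can add subjects, and the interim rates already count missing as TG.

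All five limit the size of the effect, and none removes the point. The documents do not say that 50% and 10% include missing readings; SAP 2.5 gives them directly after the pilot rates, which came from subjects with follow-up biopsies. Re-estimation targets only 60% conditional power, so it reduces the loss without being designed to restore 90%. The planned Fisher/CHW test at 15+15 is below 90% even with complete data.

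SAP section 17 records that the sponsor stopped the study for futility after the first interim analysis. The point therefore concerns the plan's stated power and how it is reported.

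**Conclusion.** The concern holds in a conditional form. The primary sizing states at least 90% power with no stated allowance for missing Month 6 readings, while the analysis counts them as TG in both arms. If 50% and 10% are rates among assessed subjects, power is lower than stated by an amount that depends on the test and the missing fraction. For single Fisher the loss runs from under 2 points at 1.3% missing to about 7 points at 5% and 14.5 points at 10%, with the missing readings inside the 60. It is smaller if they are extra to the 60. For pooled Z the loss is about 5 points at 5%, which leaves about 90%.

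The planned test without re-estimation gives 85.1% with none missing and 76.5% at 5%. The gap to 90% with none missing comes from combining two stagewise Fisher tests, not from missing data.

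All these figures assume equal missingness in the two arms, independent of TG. The documents do not support an unconditional statement that power is 84%.

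**What to change.** In SAP 2.5 and Protocol 9.6:

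1. Name the test used for the primary sizing.
2. State the assumed fraction of missing or insufficient Month 6 readings, and whether 50% and 10% already include it.
3. Restate the primary power for the planned Fisher/CHW test under the missing-equals-failure rule, over a range such as 0 to 10% missing. Say whether missing subjects lie within the 60 or are added to it, and whether re-estimation is included.

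The cost is a few sentences and a less favourable figure. If the assumed rates do include missing subjects, saying so settles item 2.

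A later second-interim trigger is optional and not part of this correction. With 41 per arm (15 + 26, weights set to match), the CHW test gives 92.9% at 5% missing but only 89.2% at 10%. It would use Month 6 biopsies already mandated in the 112 planned subjects, at the price of a later readout.

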## 2.6 Multiplicity Adjustments for Type I Error Control

To control the overall Type I error, the primary and key secondary endpoint will be tested hierarchically with a fixed sequence approach. The study will continue to assess the key secondary endpoint only if the primary null hypothesis has been rejected. Thus, the significance of the key secondary endpoint is contingent, and no adjustment for multiple endpoints is needed.

The primary endpoint will have 2 analyses (1 interim and 1 final for the primary endpoint). The first interim analysis is for futility and sample size recalculation. The second interim analysis, which serves as the final analysis for the primary endpoint, is for the assessment of efficacy (new or worsening TG at 6 months). The alpha level of 0.0001 is to be spent at the first interim

analysis in developing the efficacy boundary of the second interim analysis of TG at 6 months. The overall significance level for the efficacy analysis of primary endpoint will be preserved at 0.025 (1-sided test) by using a significance level of 0.0249 for the second interim analyses. The difference between treatments will be evaluated by using the CHW weighted test statistic (Cui et al., 1999).

The key secondary endpoint will have 3 analyses (2 interim and 1 final), at approximately 50% (~26 events), 75% (~39 events) and 100% (~51 events) of the targeted all-cause graft failure. The Hwang-Shih-DeCani alpha spending function with phi = -4, which is similar to the boundaries from the O'Brien-Fleming method, will be used for the unequal spaced timing of analysis. Using this approach requires  $z \geq 2.75$  (or equivalently  $p \leq 0.0030$ ) to consider stopping the study for a positive treatment effect at the first interim analysis (~50% of events),  $z \geq 2.43$  (or equivalently  $p \leq 0.0075$ ) to consider stopping the study for a positive treatment effect at the second interim analysis (~75% of events), and  $z \geq 2.01$  (or equivalently  $p \leq 0.0221$ ) to claim efficacy at the final analysis (~100% of events), as shown in the table below. This approach maintains a fixed sample p-value close to 0.025 (1-sided test) at the final analysis and an overall significance level at 0.025.

Analysis	Proportion of Targeted Number of Events	Z Scale	p-value (1-sided)
Interim 3	50%	2.751	0.0030
Interim 4	75%	2.428	0.0075
Final	100%	2.012	0.0221

### **3. OBJECTIVES**

#### **3.1 Primary Objective**

The primary objective of this study is to evaluate the efficacy of CINRYZE administered with plasmapheresis, plasma exchange, or immune adsorption treatments and sucrose-free immunoglobulin (IVIg) for the treatment of acute AMR of renal allograft in kidney transplant recipients as measured by the proportion of subjects with new or worsening transplant glomerulopathy (TG) at 6 months after treatment initiation.

#### **3.2 Secondary Objectives**

The key secondary objective is to evaluate the efficacy of CINRYZE administered with plasmapheresis, plasma exchange, or immune adsorption treatments and sucrose-free IVIg for the treatment of acute AMR of renal allograft in kidney transplant recipients as measured by the proportion of subjects with all-cause graft failure at 4 years following treatment initiation for the initial qualifying AMR episode.

[figure not shown]
Secondary objectives from study entry to 6 months are:

- To assess renal function
- To assess proteinuria
- To assess change in histopathology
- To assess graft outcomes

Secondary objectives from study entry to graft failure or 4 years:

- To assess renal function
- To assess proteinuria
- To assess graft outcomes
- To assess resolution of AMR
- To assess safety and tolerability of CINRYZE in kidney transplant recipients
- To assess subject survival status

**3.3      Exploratory Objectives**

## **4. SUBJECT POPULATION SETS**

### **4.1 All-enrolled Set**

The All-enrolled Set will consist of subjects who have signed informed consent.

### **4.2 Intent-to-Treat Set (ITT)**

The Intent-to-Treat Set will consist of all subjects in the All-enrolled Set for whom a randomization number has been assigned. This set will be used for sensitivity analyses of efficacy endpoints provided that the ITT set differs by the FAS by at least 10%

### **4.3 Full Analysis Set (FAS)**

The Full Analysis Set will consist of all subjects who have taken at least 1 dose of investigational product. The FAS will be used for efficacy analysis according to assigned treatment.

### **4.4 Safety Analysis Set (SAF)**

The Safety Analysis Set will consist of all subjects who have taken at least 1 dose of investigational product. The Safety Analysis Set will be used for safety analysis according to actual treatment received.

### **4.5 Per-protocol Analysis Set-1 (PPS1)**

The Per-protocol Analysis Set-1 will consist of all subjects in the FAS who have taken at least 5 of the 7 planned doses, are assessed for TG at 6 months after initiation of treatment or have post-baseline biopsy-proven new or worsening TG within 6 months of initiation of treatment, and do not have predefined major protocol deviations that may affect the primary efficacy endpoint.

These protocol deviations will be identified prior to unblinding of the study.

### **4.6 Per-protocol Analysis Set-2 (PPS2)**

The Per-protocol Analysis Set-2 will consist of all subjects in the FAS who have taken at least 5 of the 7 planned doses, are assessed for graft failure at 4 years, or have shown graft failure within 4 years, or died, and do not have predefined major protocol deviations that may affect the key secondary endpoint.

These protocol deviations will be identified prior to unblinding of the study.

#### **4.7 Pharmacokinetic and Pharmacodynamic Analysis Set**

- PK Analysis Set: all subjects who have at least 1 reported post dose PK concentration value. All PK analyses will be based on the PK Set. The Clinical pharmacology group will identify the PK analysis set.
- PD Analysis Set: all subjects who have at least 1 reported post dose PD value. All PD analyses will be based on the PD Set. The Clinical pharmacology group will identify the PD analysis set.

